### 6.2. Protection of Vulnerable Subjects

The information collected in this study could not have been obtained in a less vulnerable, consenting population, necessitating the use of minor patients. Adolescent, pediatric, and neonatal patients will be recruited and enrolled according to all US FDA, ISO 14155:2011 GCP, and other applicable local requirements for protection of vulnerable subjects. Special measures will be taken to protect the rights of these vulnerable study participants and to shield them from undue risk. Study procedures for pediatric and neonate subjects will be modified to minimize interruption in normal medical care, which includes additional limitations on sampling frequency beyond the minimums suggested by ISO 81060-2:2013 (as shown in Table 2) for the general population. This is done to ensure minimal risk for participating subjects.

### 6.3. Number of Subjects

The total minimum enrollment for the two study arms is 83 total evaluable patients (maximum of 200 patients), as follows:

1. **PDM-SuperSTAT Arm ( $N_{PDM}$ ):** 45 evaluable patients with GE DINAMAP® SuperSTAT algorithm (PDM Module) on CARESCAPE Monitor B650, to achieve a total target of  $\geq 150$  BP data pairs in patients  $\geq 3$  years old (up to 10 paired measurements per subject) and  $\geq 150$  BP data pairs in patients  $< 3$  years old (as described in Table 2).
2. **PSM-Datex-Ohmeda Arm ( $N_{PSM}$ ):** 29 evaluable patients with Datex-Ohmeda algorithm (PSM module) on CARESCAPE Monitor B650, to achieve a total of  $\geq 150$  BP data pairs in patients  $\geq 3$  years old (up to 10 paired measurements per subject) and  $\geq 150$  BP data pairs in patients  $< 3$  years old (as described in Table 2).

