## 5.2. Controls and Minimization of Bias

Patients will be enrolled consecutively into the PDM-SuperSTAT study arm and, if stratification quotas are met, then into the PSM-Datex-Ohmeda study arm until each arm's stratification quota reaches its minimum allotment. Thereafter, patients may be enrolled consecutively without regard to stratification quota until the minimum total patient population is reached. Consecutive enrollment is designed to limit selection bias. The devices with algorithms and required peripherals, including cuffs and hoses, will be provided by the Sponsor to ensure consistency between procedures and limit possible bias due to variations in storage, handling, or lot numbers.

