### 6.3.1. Stratification of Subjects

Subject enrollment will be stratified based on prospective criteria to ensure diversity in the population, as described in ISO 81060-2:2013 and set forth in Table 1. Patients will be enrolled concurrently in both arms until all minimum quotas are reached, and thereafter up to the maximum enrollment for the study. Incomplete/non-evaluable datasets, as determined by the Sponsor, will not be considered to satisfy minimum requirements in Table 1. Additionally, multiple cuff sizes will be used, including a minimum of  $1/(2 \times n)$  per stratification group (except for the children/infants/neonates group), where  $n$  is the total within a stratification group able to be tested using the cuff in accordance with its labeling (Table 1).

**Table 1** – Summary of Patient Enrollment Stratification by Characteristics

Enrollment Stratification	Minimum Total in PDM-SuperSTAT arm	Minimum Total in PSM-Datex-Ohmeda arm	Age (years) requirement	Weight (g) requirement	Gender (M/F)	Minimum number of patients (n)	
Adults and Adolescents (General population) b	15 total patients	15 total patients	>12 yr	(no weight requirement)	F #	$n \geq 5$	
			>12 yr		M #	$n \geq 5$	
Adults and Adolescents Chronic Atrial Fibrillation b	7 total patients	-	>12 yr		M or F #	$n \geq 7$	
Pediatrics	5 total patients	5 total patients	$\geq 3$ AND $< 12$ yr		F #	$n \geq 2$	
			$\geq 3$ AND $< 12$ yr		M #	$n \geq 2$	
Children/Infants/ Neonates	18 total patients	-	$\geq 1$ yr AND $< 3$ yr		M or F	$n \geq 3$	
			>29 days AND $< 1$ yr		M or F	$n \geq 3$	
			(no age requirement)*		< 1000 g	M or F	$n \geq 3$
					1000-2000 g	M or F	$n \geq 3$
	-	9 total patients	>2000 g		M or F	$n \geq 3$	
			$\geq 1$ yr AND $< 3$ yr	>5 kg (~11 lbs) a	M or F	$n \geq 3$	
			>29 days AND $< 1$ yr	>5 kg (~11 lbs) a	M or F	$n \geq 3$	
			(no age requirement)*	>5 kg (~11 lbs) a	M or F	$n \geq 3$	
TOTAL	45 TOTAL	29 TOTAL					

**Abbreviations:** M = male; F = female;  $n$ , number of patients

\* No age requirement within the children/infant/neonates category may include subjects aged birth to  $< 3$  yrs

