## 6.6. Screening Subjects for Enrollment

There are three (3) investigational clinical sites involved in this clinical trial. Patients will be screened for enrollment by the investigational site according to their standard procedure, in accordance with IRB policy. All patients will be consecutively screened and enrolled first into the PDM-SuperSTAT group if eligible. Remaining patients will then be screened for the PSM-Datex-Ohmeda group. All patient enrollment will be conducted according to the stratification criteria and inclusion/exclusion criteria.

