5. Repeat steps 3 and 4 adhering to the requirements in [Table 2](#) until the target number of recordings and determinations have been performed or the subject leaves the study. In the event that any blood pressure determination is not successful, the procedure may be repeated to achieve the target number of successful blood pressure determinations. No more than the maximal number of total blood pressure determinations as specified in [Table 2](#) will be performed on any patient.
6. When all NIBP measurements are complete, stop the IBP data collection.

For PDM procedures where the PDM Data Collection Module is used, data may be captured electronically instead of using the manual procedure according to the following procedure:

1. Use the PDM Data Collection Module to determine the patient's blood pressure.
2. Wait at least 3 min.
3. Simultaneously record and determine the patient's blood pressure, as follows.
  - a. Start NIBP measurement from the PDM Data Collection Module
4. Wait the appropriate amount of time between determinations (as defined in [Table 2](#)).
5. Repeat steps 3 and 4 adhering to the requirements in [Table 2](#) until the target number of recordings and determinations have been performed or the subject leaves the study. In the event that any blood pressure determination is not successful, the procedure may be repeated to achieve the target number of successful blood pressure determinations. No more than the maximal number of total blood pressure determinations as specified in [Table 2](#) will be performed on any patient.
6. When all NIBP measurements are complete, stop the data collection.

The same number and type of determination should be performed whether the manual or digital PDM Data Collection Module is used.

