**Table 2 – Number of Blood Pressure Assessments and Frequency**

Population	Maximum Number of BP Determinations	Target Number of Valid BP Determinations	Frequency of Determinations
Pediatric, Adolescents, and Adults (aged ≥ 3 years)	15 max attempts	10 determinations	At least 60 s between determinations
Children & Infants (<3 years old to >29 days old)	10 max attempts	10 determinations	At least 60 s between determinations
Neonates (< 29 days old)	10 max attempts	5-10 determinations	At least 3 minutes between determinations (over max of 72 hours)

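### The arm minima sum to 74 against a stated total of 83, and the minimum of 9 PSM patients under 3 years yields at most 90 of the 150 pairs set for them, with no stratum-closing rule that refers to pairs

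*Combined protocol and SAP*

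**What the plan says.** **Patient numbers.** Section 6.3 opens with "The total minimum enrollment for the two study arms is 83 total evaluable patients (maximum of 200 patients), as follows", and two items come after it. The PDM arm has 45 evaluable patients. The PSM arm has "29 evaluable patients with Datex-Ohmeda algorithm (PSM module) on CARESCAPE Monitor B650, to achieve a total of" at least 150 pairs in patients aged 3 or over and at least 150 in patients under 3. The PDM arm carries the same two pair targets. Table 1 (Section 6.3.1) repeats the arm totals of 45 and 29. For PSM patients under 3, all over 5 kg, it requires "9 total patients".

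**Pairs per patient.** Section 7.2.4 makes Table 2 a hard limit: "No more than the maximal number of total blood pressure determinations as specified in" that table may be made on a patient. For both groups under 3 years Table 2 gives "10 max attempts". The target is 10 determinations for those older than 29 days and 5 to 10 for neonates. Section 9.3.1 discards anything after the tenth valid measurement, and Section 6.5 bars a second participation.

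**When enrolment stops.** Section 5.2 says that once the quotas are filled "patients may be enrolled consecutively without regard to stratification quota until the minimum total patient population is reached". Section 6.3.1 says "Patients will be enrolled concurrently in both arms until all minimum quotas are reached, and thereafter up to the maximum enrollment for the study". Section 6.6 says "All patients will be consecutively screened and enrolled first into the PDM-SuperSTAT group if eligible". Section 7.4 leaves opening and closing of a stratum to the sponsor, having regard to regulations and standards. Section 9.6 ties a pass to a data set adequate for ISO 81060-2:2013. None of these gives a number of pairs.

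**Missing data.** Section 9.5 expects no missing pressures because up to 15 attempts may be made to get 10 recordings.

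**The concern.** Section 6.3 presents the total and the two arm sizes as one set of figures, yet they do not add up. It also presents the PSM arm size as the means to its pair targets, yet for the under-3 group the patient minimum and the per-patient limit together fall short of the target.

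PSM children under 3 are one of the four populations analysed separately in Section 9.1.1, and the primary objective covers all indicated populations. Accuracy in this group is judged on the mean and SD of the errors over its own pairs. If patient counts alone decide when the stratum is full, it can be recorded as complete with well under the planned amount of data.

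**Working it through.** **Step 1. The stated total.** Inputs are the stratum minima in Table 1.
- PDM: 15 + 7 + 5 + 18 = 45, as stated.
- PSM: 15 + 5 + 9 = 29, as stated.
- Sum: 45 + 29 = 74. Section 6.3 says 83; the difference is 9.

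The arm totals reproduce, but the overall total does not. For information only: 45 + 38 = 83, and 38 is the superseded PSM number that Appendix E, item 93, changed to 29.

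**Step 2. Capacity at the patient minima.** Maximum pairs = patients × 10, since attempts, analysed measurements and participations are all capped.

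| Population (Section 9.1.1) | Minimum patients | Maximum pairs | Target |
|---|---|---|---|
| PDM, 3 or over (incl. atrial fibrillation) | 15 + 7 + 5 = 27 | 270 | 150 |
| PSM, 3 or over | 15 + 5 = 20 | 200 | 150 |
| PDM, under 3 | 18 | 180 | 150 |
| PSM, under 3 | 9 | 90 | 150 |

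PSM under 3 reaches 90/150 = 60%, a shortfall of at least 60 pairs. Nine patients would each need 150/9 = 16.7 pairs, above the cap of 10.

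**Step 3. Can the target be met at a total of 83?** If a of the 9 patients between 74 and 83 fall in this stratum, capacity is (9 + a) × 10: 90 for a = 0, 150 for a = 6, 180 for a = 9.
- All figures met: 45 PDM + 38 PSM with 18 under 3. Capacity is 180, so 150/180 = 83% of attempts must be valid.
- All patient minima met, pair target missed: 54 PDM + 29 PSM = 83, with 9 under 3 and at most 90 pairs.

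**Step 4. Patients needed for 150 pairs.** With every attempt valid, 150/10 = 15. That makes PSM 15 + 5 + 15 = 35 and the sum 45 + 35 = 80. The documents give no rate of valid attempts. Under assumed rates:
- 90% valid: 150/9 = 16.7, so 17 (PSM 37, sum 82).
- 80% valid: 150/8 = 18.75, so 19 (PSM 39, sum 84).

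These counts meet 150 only on average. If attempts are also assumed independent, the chance of at least 150 pairs is 0.82 for 17 patients at 90% and 0.68 for 19 at 80%. No patient count alone guarantees the target.

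**Step 5. PDM under 3.** The 180 in Step 2 is capacity, not expected yield, because a neonate may stop at 5. With k of the 18 stopping at 5, the maximum is 180 − 5k, which is below 150 once k is 7 or more. For an assumed mix of 9 neonates at 5 and 9 others at 10, it is 45 + 90 = 135.

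**Step 6. Section 9.5 against Table 2.** Fifteen attempts for 10 recordings is the Table 2 allowance for patients aged 3 or over. Under 3 the allowance is 10, so when the target is 10 a failed attempt cannot be replaced.

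**The case against.** **83 may be deliberate.** The last enrolment step in Section 5.2, filling up to a total without regard to quotas, would do nothing if the total equalled the summed quotas. Table 1 also has component rows below their stratum total: adults 5 + 5 = 10 under 15, pediatrics 2 + 2 = 4 under 5, PDM under 3 years 5 × 3 = 15 under 18. So a reader who infers that 83 must be an error goes further than the text allows. Against that, the strata add exactly to both arm totals, Section 6.3 introduces the arms as the breakdown of 83, and nowhere is 83 called an additional floor.

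**The target is not out of reach or without protection.** A reader might infer that the design makes 150 pairs impossible, or that nothing at all guards against a shortfall. Neither is supported. Section 6.3 states the target. Section 6.3.1 has enrolment continue up to the maximum, which is 200. Section 7.4 lets the sponsor keep a stratum open in the light of standards, and Section 9.6 ties passing to the ISO standard. What is missing is narrower: a stratum-closing rule that refers to the pair target.

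**The 54 + 29 case is an extreme.** It needs enrolment to stop at 83 and all nine extra patients to go to PDM. That fits Sections 5.2 and 6.6 more easily than the concurrent enrolment in Section 6.3.1. It shows what the rules permit, not what is likely.

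**Non-evaluable data sets do not count.** Section 6.3.1 excludes them from the minima. Even if an evaluable patient meant one with 10 valid pairs, nine would still give 90.

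**Section 9.5 is a wording slip.** It is: incomplete pairs are excluded in any case, so the analysis method does not change. But its reassurance about missing pairs is wrong for the under-3 groups.

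**Conclusion.** The point holds. The arm minima sum to 74, not 83, and whether 83 is a separate floor is left unstated. The PSM under-3 minimum of 9 cannot deliver its own target: the ceiling is 90 of 150 pairs, at least 60 short. This follows from limits in the documents and needs no assumption.

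The target can be reached if the stratum stays open to at least 15 patients, which the enrolment rules allow. They do not make closure depend on it, so every patient minimum can be satisfied without it. PDM under 3 has the capacity but can also fall short if enough neonates stop at 5 determinations; how many would do so is not known.

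It should not be inferred that 90 pairs would fail ISO 81060-2:2013. The standard is not among the documents, so that cannot be judged here. Any patient count above 15 rests on an assumed rate of valid attempts.

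**What to change.** 1. Restate the minima and pair targets in Section 6.3 and Table 1 as one consistent set.
   - If 150 pairs stands, the PSM under-3 minimum must be at least 15 (PSM 35, sum 80), and higher if some attempts are expected to be invalid.
   - If 9 patients stands, say that the arm minima sum to 74 and that 9 patients give at most 90 pairs. Restate the pair target only after checking it against ISO 81060-2:2013. Ninety itself would not be a workable target, since one invalid attempt among 9 patients would miss it.
   - In either case, say explicitly whether 83 is a separate floor above the summed quotas.
2. State that each under-3 population, PSM and PDM, is complete only when both its patient minimum and its stated pair target are met.
3. Limit the 15-attempt sentence in Section 9.5 to patients aged 3 or over.

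Items 1 and 3 are corrections to text and a table; item 2 adds one closing rule. The real cost comes with keeping 150 pairs: at least 15 − 9 = 6 more PSM children under 3 than the Table 1 minimum, within the cap of 200. For those catheterised under general anaesthesia, Section 2.3.2 says that taking part may lengthen it by about 25 minutes.

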### 6.3.1. Stratification of Subjects

Subject enrollment will be stratified based on prospective criteria to ensure diversity in the population, as described in ISO 81060-2:2013 and set forth in Table 1. Patients will be enrolled concurrently in both arms until all minimum quotas are reached, and thereafter up to the maximum enrollment for the study. Incomplete/non-evaluable datasets, as determined by the Sponsor, will not be considered to satisfy minimum requirements in Table 1. Additionally, multiple cuff sizes will be used, including a minimum of  $1/(2 \times n)$  per stratification group (except for the children/infants/neonates group), where  $n$  is the total within a stratification group able to be tested using the cuff in accordance with its labeling (Table 1).

**Table 1** – Summary of Patient Enrollment Stratification by Characteristics

Enrollment Stratification	Minimum Total in PDM-SuperSTAT arm	Minimum Total in PSM-Datex-Ohmeda arm	Age (years) requirement	Weight (g) requirement	Gender (M/F)	Minimum number of patients (n)	
Adults and Adolescents (General population) b	15 total patients	15 total patients	>12 yr	(no weight requirement)	F #	$n \geq 5$	
			>12 yr		M #	$n \geq 5$	
Adults and Adolescents Chronic Atrial Fibrillation b	7 total patients	-	>12 yr		M or F #	$n \geq 7$	
Pediatrics	5 total patients	5 total patients	$\geq 3$ AND $< 12$ yr		F #	$n \geq 2$	
			$\geq 3$ AND $< 12$ yr		M #	$n \geq 2$	
Children/Infants/ Neonates	18 total patients	-	$\geq 1$ yr AND $< 3$ yr		M or F	$n \geq 3$	
			>29 days AND $< 1$ yr		M or F	$n \geq 3$	
			(no age requirement)*		< 1000 g	M or F	$n \geq 3$
					1000-2000 g	M or F	$n \geq 3$
	-	9 total patients	>2000 g		M or F	$n \geq 3$	
			$\geq 1$ yr AND $< 3$ yr	>5 kg (~11 lbs) a	M or F	$n \geq 3$	
			>29 days AND $< 1$ yr	>5 kg (~11 lbs) a	M or F	$n \geq 3$	
			(no age requirement)*	>5 kg (~11 lbs) a	M or F	$n \geq 3$	
TOTAL	45 TOTAL	29 TOTAL					

**Abbreviations:** M = male; F = female;  $n$ , number of patients

\* No age requirement within the children/infant/neonates category may include subjects aged birth to  $< 3$  yrs

# Investigators should equitably represent male and female patients, which must each make up a minimum of 30% of the final population upon completion (i.e. at least 30% male and 30% female, the remaining may be either male or female based on enrollment).

**Important: Additional Stratification requirements**

a Only patients weighing  $> 5$  kg (approximately 11 lbs) can be examined with PSM-Datex-Ohmeda under the current labeling

b Among adult/adolescents, at least 10% should have baseline systolic BP of  $\leq 100$  and  $\geq 160$  as well as diastolic BP of  $\leq 70$  and  $\geq 85$  mmHg

## 6.4. Inclusion Criteria

Subjects will be included that:

1. Are aged >29 days requiring clinically indicated non-emergent heart catheterization OR aged ≤29 days with placed or scheduled placement of an indwelling femoral, radial, or umbilical arterial monitoring line;
2. Have an upper limb (right OR left side) that fits a cuff size of the device (circumference ranging 3 cm to 40 cm) OR have a thigh (right OR left side) that fits a cuff size of the device (circumference ranging 38 to 50 cm);
3. Are expected to be able to provide blood pressure measurements using both IBP and NIBP;
4. Are able and willing to provide written informed consent or have a legally authorized representative willing to provide written informed consent with assent from minor patients, as required by IRB policy.

## 6.5. Exclusion Criteria

Subjects will be excluded that:

1. Have previously participated in this study (no subject may participate more than once).
2. Exhibit signs or symptoms or have a current diagnosis of peripheral vascular disease in upper AND/OR lower limbs;
3. Have current, uncontrolled circulatory shock;
4. Exhibit injuries, deformities, intravenous lines, or other abnormalities that, in the opinion of the investigator, may prevent proper cuff application or functioning;
5. For women of child-bearing potential, are currently pregnant, suspected to be pregnant, or are currently lactating;
6. Have any condition that could interfere with the subjects ability to tolerate the procedure, including having a maximum of 4 fast flushes (adult, adolescent, or pediatric patients aged >29 days) or 1 fast flush (neonates aged <29 days);
7. If aged greater than 29 days but less than 12 years of age, have previously had any clinical or research procedure requiring general anesthesia in the last 3 month period;
8. If aged greater than 29 days but less than 12 years of age, are expected to require more than three (3) total hours of continuous general anesthesia for the scheduled procedure (including clinically necessary anesthesia and anticipated 25 minute extension for study purposes).

## 6.6. Screening Subjects for Enrollment

There are three (3) investigational clinical sites involved in this clinical trial. Patients will be screened for enrollment by the investigational site according to their standard procedure, in accordance with IRB policy. All patients will be consecutively screened and enrolled first into the PDM-SuperSTAT group if eligible. Remaining patients will then be screened for the PSM-Datex-Ohmeda group. All patient enrollment will be conducted according to the stratification criteria and inclusion/exclusion criteria.

## 7. PROCEDURES FOR RESEARCH STUDY

### 7.1. Setup Procedures

#### 7.1.1. IBP Data Collection on the Data Collection System (DCS)

The PDM Data Collection Module may be used to collect research data (based on availability) for PDM procedures, else IBP and ECG data will be collected using a DASH® 4000 patient monitor with the hardware and software tools to connect to a computerized data collection system (DCS) housed on a Sponsor-provided laptop computer. A laptop will be connected for electronic data capture, when GxP-validated data capture tools are used. The investigator is responsible for setting up the data collection according to the “Setup of Data Collection” section of the *Device Set-Up Manual* provided by the Sponsor. For applicable procedures, the control panel for the DASH® 4000 patient monitor is shown in the “DASH® 4000 Control Panel” section of the section of the *Device Set-Up Manual* provided by the Sponsor, which provides details on user setup and operation of the DASH® 4000 patient monitor.

The patient procedure for IBP setup is shown in the “IBP Setup” section of the *Device Set-Up Manual* provided by the Sponsor. Similarly, the *Device Set-Up Manual* provides instructions for setup and use of the PDM Data Collection Module for electronic data capture during PDM procedures.

#### 7.1.2. NIBP Data Collection

NIBP will be recorded on a commercial CARESCAPE Monitor B650 with most recent commercial software version installed. NIBP data will be transcribed by hand from the display of the CARESCAPE B650 monitor onto the Sponsor-provided Case Report Form (CRF) when the PDM Data Collection Module is not available. When the PDM Data Collection Module is available, data collection may be performed electronically using this tool.

For patients in the PDM-SuperSTAT arm of the study, NIBP will be measured with a CARESCAPE Monitor B650 equipped with a PDM acquisition module or the GxP PDM Data Collection Module. For patients in the PSM-Datex-Ohmeda arm of the study, NIBP will be measured with a CARESCAPE Monitor B650 equipped with a PSM acquisition module.

